Results: Our results showed that Silodosin turned out to be better in expulsing stone as well as in producing lesser side effects and hence better safety profile than Tamsulosin. Silodosin showed greater stone expulsion rate with about 55 patients expulsing stone in less than 14 days in comparison to just about 5 patients on Tamsulosin. Similarly, patients on Silodosin, showed lesser side effects as compared to Tamsulosin. Nine patients on tamsulosin (60.0%) and six patients on silodosin (40.0%) developed orthostatic hypotension. Only a very tiny percentage of patients reported abnormal ejaculation; two individuals on tamsulosin (66.7%) and one patient on silodosin (33.3%). Another side effect that was identified involved headaches, seen by four patients on silodosin (44.4%) and five patients on tamsulosin (55.6%).

INTRODUCTION

Stone disease is one of the most frequent presentations in the field of urology. A large number of these patients arrive with ureteric stones(1). Globally, occurrence of stone formation is 10-12% for men and 6-8% for women. Its prevalence in Pakistan is approximately 16%. The disease's burden has increased in all age categories and both genders over the past 20 years(2). The incidence of urolithiasis in different age groups is 12.2% in the persons 20-29 year old, 29.6% in those who are 30-39-year-old, and 31.5% in 40–49-year-old patients(3).

Medical management ae well as surgical removal are various options available for treating ureteric stones as per American Urology Association (AUA) and European Association of Urology (EAU) guidelines. However, due to risks of surgical approaches there is always an attempt for treatment by using medical expulsive treatment (MET) for ureteric stones first keeping in view different parameters. According to European Association of Urology Guidelines (EAU), the ureteric stones less than 10 mm can be treated with MET(4). Medical expulsive therapy (MET) is a well-established treatment option for distal ureteric stones, despite a sharp increase in minimally invasive techniques(5). Stones smaller than 5 mm have passage rates ranging from 71% to 98%, while stones with size more than 5 mm had expulsion rates ranging from 25% to 53%(6).

Many factors affect stone removal and must be considered while selecting MET for stones like ureteric spasm, location, size, and number of stones and duration for which it is present and also the ureteric architecture etc(7).

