It is hypothesized that efficacy and safety of medical expulsive therapy, containing tamsulosin and silodosin, is almost the same and silodosin can be used with the same efficacy for the treatment of lower urinary tract calculi.

Alternative Hypothesis:

Silodosin is better than Tamsulosin in efficacy and safety.

OPERATIONAL DEFINITIONS:

STONE CLEARANCE:

Stone clearance will be defined as no evidence of stone on follow up X-ray KUB imaging at 4 weeks .

ANCILLARY PROCEDURES:

Additional urological procedures needed to remove the same stone for which medical expulsive therapy was given if it fails to remove the stone completely.

SIDE EFFECTS:

Any undesirable effect noticed after prescription of the drug including but not limited to abnormal ejaculation, headache, orthostatic hypotension, backache and gastritis etc.

MATERIALS AND METHODS:

STUDY DESIGN:

Prospective randomized control trial.

STUDY SETTING:

Outpatient department of Sir Ganga Ram hospital, Lahore.

DURATION OF STUDY:

18 months.

DURATION OF TREATMENT:

Four weeks.

SAMPLE SIZE:

Using the open-epic software, the sample size was estimated. The minimum sample size that we require is 208 patients with ureteric stone who fulfil the inclusion criterion with 104 in one group receiving tamsulosin and 104 in silodosin group (1:1 ratio) with an inflation of 10 percent for estimated loss to follow up, with an anticipated expulsion rate ranging from 58-64 percent in tamsulosin group and 78-83 percent in silodosin group with a risk difference of 19 to achieve a power of 80 percent and a level of significance of 5 percent.

SAMPLING TECHNIQUE:

Patients visiting the outpatient department of Sir Ganga Ram hospital will be selected by simple random sampling, fulfilling the inclusion criteria.

SAMPLE SELECTION:

Adult male and female patients fulfilling the inclusion criteria will be assigned into two groups by random allotment, 1^{st} group will be given Tamsulosin and 2^{nd} group will be given Silodosin for four weeks.

INCLUSION CRITERIA:

Following factors make up the inclusion criteria for this study.

- Patients between ages 18 years 55 years.
- Solitary unilateral ureteral stone
- Stone sizes less than 10 mm measured on non-contrast computed tomography of kidney, ureter and bladder.
- Stones being treated primarily with medical expulsive therapy
- Radio opaque Stone

EXCLUSION CRITERIA:

The presence of following factors will exclude the patients from our study:

- Pregnancy
- Untreated UTI

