- Bleeding disorders
- Obstruction distal to stone
- Serum Creatinine > 1.3 mg/dl in males and > 1.2 mg/dl in females.
- Congenital renal anomaly/ skeletal malformation
- Previous treatment for the same stone (PCNL/ URS / push back)
- Solitary Kidney
- Prior JJ stent insertion
- Bilateral ureteral stone

DATA COLLECTION AND PROCEDURE:

The protocol will be submitted to Ethical review committee for review and only once the permission is granted, the study will be started. Patients will undergo standard procedure like detailed history taking, examination and routine investigations. Once decided that the patient will undergo MET, the patient will be explained in detail about medications, their potential side effects, follow up and the potential indications for early follow up. Our study will not change any standard process in place except the randomization between Tamsulosin and Silodosin. The data will be kept confidential as a top priority. Only principal investigator and co-principal investigator will have access to the data.

All patients as per inclusion and exclusion criteria as described above will be included in the study. The CT scan (non contrast computed tomography) will be done on (machine parameters at Ganga ram). Only patients with radioopaque stones will be included. Patients falling into the inclusion criteria will be explained about the study and once they agree to participate in study, randomization will be done. Demographic data including patients' age and comorbid, stone-related data including size, location, laterality and number of stones and duration of symptoms will be recorded. The patient will be given either Capsule Tamsulosin 0.4 mg once daily at night or Tablet Silodosin 8 mg once daily at night based on the group assigned. The patient will also be explained about the reasons for follow up earlier than four weeks including fever, persistent pain or gross hematuria. The patients will be called for follow up at 4 weeks with an X-ray KUB without bowel preparation. We will note if the stone has passed or not.

ETHICAL CONSIDERATION:

The funds for supporting this research will be provided by department of pharmacology and therapeutic FJMU, Lahore. Informed consent will be taken from patients prior to research.

DATA ANALYSIS PROCEDURE:

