	Mid	08(17.4%)	38(82.6%)	0.001
	Distal	41(51.9%)	38(48.1%)	
Water intake	Less than 1 litre	59(54.6%)	49(45.4%)	
	More than 1 litre	18(25.4%)	53(74.6%)	0.001
Analgesic requirement	Yes	26(61.9%)	16(38.1%)	0.005
	No	51(37.2%)	86(62.8%)	
Time for removal	Less than 14 days	6(10.3%)	52(89.7%)	
	14-21	14(27.5%)	37(72.5%)	0.001
	22-28	57(81.4%)	13(18.6%)	

presented as frequency and percentage with association

The table compares several factors along with the corresponding p-values to assess statistical significance between two drugs tamsulosin and silodosin.

First, based on Body Mass Index (BMI), 43.4% of those with a normal BMI were prescribed Tamsulosin, while 56.6% were recommended Silodosin. On the other hand, among those who were obese, 38.5% were given Tamsulosin and 61.5% were given Silodosin; p-value came out to be 0.730, which meant that there was no statistically significant variation in the medication preferences according to BMI.

15.2% of patients who had pain for more than a week prior to CT scan, received Tamsulosin while 84.8% received silodosin.

51.9% of the patients with proximal ureteric stone were given Tamsulosin and 48.1% received Silodosin.

82.6 percent of patients with mid-ureteric stone problems received Silodosin, while 17.4% received Tamsulosin.

51.9% of patients with distal ureteric stones received Tamsulosin and 48.1% on Silodosin.

Only 38.1% of patients on Silodosin required analgesics, whereas 61.9% of patients on Tamsulosin used analgesics.

89.7% of patients on silodosin had their stone removed in less than 14 days, while only 10.3% of the patients on Tamsulosin had their stone removed in aforementioned duration.

72.5% of patients on Silodosin had their stone removed in 14-21 days, while only 27.5% of the patients on Tamsulosin had their stone removed in same duration.

Moreover, 81.4% on Tamsulosin had their stone removed in 22-28 days and 18.6% patients on Silodosin had it removed in same duration.

		Tamsulosin	Silodosin	p- value
Side	None	61 (40.1%)	91(59.9%)	
effect	Othostatic	09 (60.0%)	06(40.0%)	
	hypotension			0.3.15
	Abnormal	2(66.7%)	1(33.3%)	
	ejaculation			
	Headache	5(55.6%)	4 (44.4%)	

Table 2 Association between Tamsulosin and Silodosin with side effects

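### The analysed arms differ far beyond chance on pre-treatment features, the allocation method is not described and the patient flow does not add up, so randomisation does not protect the unadjusted comparison

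*Combined protocol and SAP*

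**What the plan says.** Sample Selection states that adult patients "will be assigned into two groups by random allotment". Data Collection and Procedure adds that "once they agree to participate in study, randomization will be done". Neither section gives the method of generating the sequence, any blocking or stratification, a concealment procedure or any blinding. Sampling Technique says that patients "will be selected by simple random sampling, fulfilling the inclusion criteria", whereas Data Collection and Procedure says that everyone meeting the criteria enters the study.

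Sample Size sets 208 patients: "104 in one group receiving tamsulosin and 104 in silodosin group (1:1 ratio", "with an inflation of 10 percent for estimated loss to follow up". Stone size, location, laterality and symptom duration are all to be recorded. The Data Analysis Procedure offers one between-group comparison, a t-test with no covariates.

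The same document reports results. Its table of patient characteristics and study variables prints p = 0.001 for laterality, time from symptoms to CT, and position in the ureter. The accompanying text presents these as who received which drug: "15.2% of patients who had pain for more than a week prior to CT scan, received Tamsulosin while 84.8% received silodosin" and "82.6 percent of patients with mid-ureteric stone problems received Silodosin, while 17.4% received Tamsulosin". It does not discuss them as differences between randomised arms. The Conclusion states that silodosin is more successful and has a safer profile.

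**The concern.** Side of the stone, its position on CT and the length of symptoms before CT are all settled before treatment starts. Under sound 1:1 randomisation with little or even-handed loss, they should differ between arms only by chance. If they differ by much more than that, the arms were not formed as described, or patients left them selectively, or the data are wrong.

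The Introduction lists location, size and duration among the factors that affect stone removal, and it ties passage rates to size: "Stones smaller than 5 mm have passage rates ranging from 71% to 98" per cent. The headline result is time to removal. An unadjusted comparison of arms that differ on such factors could create an apparent drug effect or hide a real one, and the Conclusion rests on exactly that comparison.

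**Working it through.** **Planned arm size.** With the two-proportion formula, two-sided 5%, 80% power and 64% v 83% (the stated risk difference of 19 points):

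n = [1.96·√(2 × 0.735 × 0.265) + 0.8416·√(0.64 × 0.36 + 0.83 × 0.17)]² / 0.19² = 83.5.

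Continuity correction: (83.5/4)·[1 + √(1 + 4/(83.5 × 0.19))]² = 93.7, so 94. Then 94 × 1.10 = 103.4, so 104 per arm and 208 in all. The plan's figure is reproduced.

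**Test used.** Pearson chi-square without correction, Σ(O − E)²/E. On the BMI row (72 v 94 normal, 5 v 8 obese) it gives 0.12, p = 0.730, which is the printed value. The counts and the test are therefore read correctly.

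**Baseline rows.** The document prints row percentages. As percentages of each arm (77 tamsulosin, 102 silodosin):

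| Feature | Tamsulosin | Silodosin | Chi-square | p | p × 4 rows |
|---|---|---|---|---|---|
| Right side | 65 (84.4%) | 52 (51.0%) | 21.67, 1 df | 3.3e-6 | 1.3e-5 |
| Symptoms to CT: <1 wk / >1 wk / >2 wk | 67 (87.0%) / 10 / 0 | 37 (36.3%) / 56 / 9 | 47.14, 2 df | 5.8e-11 | 2.3e-10 |
| Position: proximal / mid / distal | 28 / 8 (10.4%) / 41 | 26 / 38 (37.3%) / 38 | 16.59, 2 df | 2.5e-4 | 0.0010 |

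For laterality: 179 × (65 × 50 − 52 × 12)² / (117 × 62 × 77 × 102) = 21.67. The last column is a Bonferroni correction over these three rows and BMI. Standardised differences, (p₁ − p₂)/√[(p₁q₁ + p₂q₂)/2], are 0.77 (right side), 1.22 (under one week) and 0.66 (mid-ureter). The rows may be correlated, so their p-values should not be multiplied together.

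**Patient flow.**
- Abstract: 104 + 104 = 208 allocated; 16 + 12 = 28 removed, leaving 180. The stated split is 89 + 93 = 182.
- Results: 179 analysed; every table row sums to 77 and 102.
- Against 104 per arm, 104 − 77 = 27 and 104 − 102 = 2 are missing (Fisher exact p = 3e-7). The Abstract's split implies 15 v 11 (p = 0.53).
- The Results have 102 on silodosin against the Abstract's 93. Loss cannot add nine patients.
- Time for removal: 6 + 14 + 57 = 77 and 52 + 37 + 13 = 102. Every analysed patient has a removal time within 28 days, so the analysed set may contain only patients who passed the stone.

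**Could loss alone explain the imbalance?** Put back the 27 and 2 missing patients so as to shrink each difference as far as possible:
- Right side: 65/104 (62.5%) v 54/104 (51.9%), p = 0.12.
- Position: 28/35/41 v 27/38/39, p = 0.91.
- Symptoms under one week: 67/104 (64.4%) v 39/104 (37.5%), chi-square 15.08, p = 1.0e-4.

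The last result does not depend on 104 per arm. Over every split of the 208 − 179 = 29 missing patients between the arms, each placed to shrink the difference, the chi-square never falls below 15.07.

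**The case against.** The strongest objection is to cause. A reader might infer that the loosely described, unstratified allotment produced the imbalance. The documents do not show that. Simple randomisation is valid, and lack of stratification does not yield p = 6e-11; if chance cannot explain the gap, something other than the described allotment did. The imbalance is also seen in the 179 analysed, not in the 208 allocated, and on an extreme assumption about the missing patients two of the three rows disappear. This objection stands, and the point is worded accordingly.

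Three further inferences are tempting and unsupported:
- That allocation was unconcealed and treatment open-label. The documents are silent. A capsule compared with a tablet, with no masking described, suggests open treatment but says nothing about concealment.
- That the imbalance favours silodosin, because its patients had longer symptoms and part of their passage time had already run. The Introduction gives duration no direction, and a stone that has not yet passed may be a harder one. Nothing says removal time is counted from the first dose. Tamsulosin had more distal stones (53.2% v 37.3%), and the Introduction places many alpha-1 receptors in the distal ureter, which might favour tamsulosin. Laterality is not named as a factor in passage.
- That 77:102 itself shows 1:1 allocation failed. For 179 patients under simple 1:1 allocation the binomial p is 0.07, and that split is of analysed patients.

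None of this restores comparability. Selective loss and data error undermine the comparison as surely as faulty allocation does.

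**Conclusion.** The point holds as a statement about the analysed comparison. The arms differ on three pre-treatment features at p = 3e-6, 6e-11 and 3e-4. Two of these, location and duration, are ones the document itself links to stone removal. The plan makes no adjustment, and the Conclusion claims superiority.

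Allocation failure, selective post-randomisation loss and data error cannot be told apart from what is printed. Loss alone could account for laterality and location; it cannot account for symptom duration. Under each explanation randomisation does not protect the comparison. Neither the size nor the direction of the resulting bias can be derived, and stone size by arm is not tabulated.

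This rests on the printed counts being correct, and on laterality, position and symptom-to-CT time being pre-treatment features, as their definitions imply. The 27 v 2 loss also assumes 104 allocated per arm. Water intake differs too (p = 1e-4), but it may have been recorded after treatment began and is not counted here.

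**What to change.** 1. Produce the allocation list and state how the sequence was generated and concealed. If no list can be produced, describe the study as a non-randomised comparison.
2. Reconcile the flow of all 208 patients by arm, with reasons for each exclusion, and resolve 104/104, 89/93 and 77/102. Tabulate baseline features as allocated, including stone size, and state what happened to patients whose stone did not pass.
3. Replace the unadjusted comparison with one adjusted for location, size and symptom duration, with laterality added as a sensitivity analysis. Report the poor overlap (0 v 9 patients in the over-two-weeks row) and say plainly that adjustment does not restore randomisation or recover missing patients.
4. Withdraw the unadjusted superiority conclusion.
5. Replace simple random sampling with consecutive eligible patients, so that Sampling Technique agrees with Data Collection and Procedure.

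For any further enrolment, use a computer-generated, concealed 1:1 list. Stratification by location or size is optional; if it is used, the analysis should include the strata.

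The covariates are already among the data to be recorded, so the cost is retrieving records, one regression analysis and rewording, with no new patients. The price is a more cautious conclusion.

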Table 2	Association between Tamsulosin and	35
	Silodosin with side effects	

LIST OF FIGURES

Serial No.	Figure	Page No
Figure 1:	Pie chart of patients using Silodosin and Tamsulosin (Medicine Advised)	33
Figure 2	Bar Chart showing comparison of stone expulsion rate in Tamsulosin and Silodosin groups	43
Figure 3	Survival function	41

L	

LIST OF ABBREVIATIONS

AUA	American Urology Association
EAU	European Association of Urology
MET	Medical expulsive therapy
PNL	Percutaneous Nephrolithotomy
RCTs	Randomized controlled clinical trials
SPSS	Statistical Package for the Social Sciences
α-AR	Alpha adrenergic receptor
LUTS	Lower Urinary Tract Symptoms

SWL	Shock wave lithotripsy
ESWL	Extracorporeal Shock Wave Lithotripsy
CKD	Chronic kidney disease
SET	Stone ejection time
USD	Ureteric stone disease
SER	Stone ejection rate

Abstract

Introduction: Ureteric stones is a very common disease world over. Medical Expulsive therapy (MET) for stones is a recognized treatment option practiced. Tamsulosin is used commonly in our population for MET however Silodosin another highly uroselective newer drug, with lesser side effects, is not used frequently for this purpose and is still under research. Both of these drugs lead to relaxation of lower ureteric smooth muscle hence facilitate in stone removal.

The rationale of this study is to compare the efficacy of Tamsulosin and Silodosin in MET (medical expulsive therapy) with regards to stone expulsion rate as well as to compare the side effect profile in our population.

Methodology: This is a prospective randomized control trial in Outpatient department of Sir Ganga Ram hospital, Lahore, on 208 patients with ureteric stone who fulfil the inclusion criterion, divided randomly into two groups with 104 patients in the Tamsulosin group and 104 patients in Silodosin group (1:1 ratio). However, 16 patients were subsequently excluded on account of premature end of study, and 12 due to being lost to follow-up (Figure 1). Out of remaining 180 patients 89 were of Tamsulosin and 93 were in Silodosin group. Demographic data including patients' age and comorbid, stone-related data including size, location, laterality and number of stones and duration of symptoms were recorded. The patients were called for follow up at 4 weeks

with an X-ray KUB without bowel preparation. We noted if the stone had passed or not.

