Data will be entered and analyzed on SPSS version 22. Percentages and frequencies will be calculated for the demographic variables of the patients. The comparison of the two groups will be made by using T- test. P-value of less than 0.05 will be considered significant and the power used will be 0.80.

RESULTS

Frequency and percentage of demographic data

Variables		Frequency	Percentage	
Gender	Male	105	58.7	
	Female	74	41.3	
Income	Less than	108	60.3	
status	50000			
	50000 -150000	69	38.5	
	Greater than	2	1.1	
	150000			
	Normal	166	92.7	
BMI	Obese	13	7.3	
	None	136	76.0	
Comorbidity	HTN	33	18.4	
	Diabetes	10	5.6	

This information sheds light on the sample population's health and demographic distribution, showing a preponderance of people with normal BMIs and lower income levels, as well as a significant percentage of people without comorbid diseases.

In our study there are total 179 patients out of which 74 are females (41.3%) and 105 males (58.7%).

The income, 108 people, or 60.3% of the total, make less than 50,000Rs in month. Just 2 members, or 1.1 percent, make more than 150,000 monthly, while 69 participants (38.5%) have monthly salaries between 50,000 and 150,000.

13 persons (7.3%) are classed as obese, while 166 people (92.7%) have a normal BMI. These numbers represent a sizable fraction of the sample. In terms of comorbidities, 136 individuals (76.0%) state they have no comorbid conditions. Of the people with comorbidities, 10 (5.6%) had diabetes, and 33 (18.4%) had hypertension (HTN).

[figure not shown]

Figure 1: Pie chart of patients using Silodosin and Tamsulosin (Medicine Advised)

Use of medicine (Figure 1)

Tamsulosin and Silodosin, the two drugs prescribed to a group of patients, are distributed as shown in the pie chart. Of the patients, 43% were advised to take Tamsulosin, which is shown as the blue section on the chart. And (57%) of the patients were advised to take silodosin, as shown by the red segment.

Table2: Patient demographic characteristics and study variables are

Varibales	Tamsulosin	Silodosin	p-value	
Body Mass index	Normal	72(43.4%)	94(56.6%)	0.730
	obese	5 (38.5%)	08(61.5%)	
Laterality	Right	65(55.6%)	52(44.4%)	0.001
	Left	12(19.4%)	50(80.6%)	
Symp To CT	Less than 1 week	67(64.4%)	37(35.6%)	
	More than 1 week	10(15.2%)	56(84.8%)	0.001
	More than 2 week	0 (0.0%)	09(100%)	
Posl n Ureler	Proximal	28(51.9%)	26(48.1%)	

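### Stone size is recorded and, on the document's own figures, strongly predicts passage, yet it is neither shown by arm nor used in any comparison, so its influence on the drug contrast cannot be checked.

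*Combined protocol and SAP*

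**What the plan says.** - **Size is named as prognostic.** The Introduction lists "location, size, and number of stones and duration for which it is present" among the factors that affect removal. It gives figures: "Stones smaller than 5 mm have passage rates ranging from 71% to 98"%. Above 5 mm, the cited range drops to 25–53%.
- **Both size bands can enter.** The Inclusion criteria require "Stone sizes less than 10 mm measured on non-contrast computed tomography".
- **Size is collected.** Data collection and procedure states that "stone-related data including size, location, laterality and number of stones and duration of symptoms will be recorded". The Abstract says the same in the past tense: "stone-related data including size, location, laterality and number of stones and duration of symptoms were recorded".
- **The analysis does not use it.** Data analysis procedure says "Percentages and frequencies will be calculated for the demographic variables of the patients" and "The comparison of the two groups will be made by using T- test". It names no covariate or stratification factor.
- **The results do not show it.** The demographic table covers gender, income, BMI and comorbidity. The two-drug table covers BMI, laterality, symptom-to-CT time, position, water intake, analgesic need and time for removal. Size and age are in neither. The captions of the figures that are not shown concern drug share, expulsion and survival. The size correlations in the Discussion carry a citation to another study.

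**The concern.** The Introduction's figures make size a strong predictor of whether a stone passes. The Discussion adds that about 95% of stones under 4 mm passed on conservative treatment alone in one cited study, and it places a 14% silodosin advantage in stones of 5–10 mm. On that account, both the outcome and the drug contrast may depend on size.

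Randomisation would normally make a large imbalance unlikely, but the features that are tabulated show arms that are not comparable. If the arms also differ in size, an unadjusted comparison mixes a size effect with a drug effect. The bias could favour either drug. The Conclusion nevertheless calls silodosin more successful without qualification, and a reader cannot test this rival explanation.

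**Working it through.** **1. The planned effect.** The Sample size section gives 104 per arm, a risk difference of 19 points, 80% power and a 5% level; sidedness is not stated, so two-sided is assumed. For 64% v 83%:

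n = [1.96·√(2·0.735·0.265) + 0.842·√(0.64·0.36 + 0.83·0.17)]² / 0.19² ≈ 84 per arm.

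With continuity correction this is 94, and 94 × 1.1 = 103.4, rounded up to 104. The stated size reproduces, so 19 points is a fair yardstick.

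**2. Are the tabulated arms comparable?** Shares within arm, from the counts in the two-drug table (77 tamsulosin, 102 silodosin):

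| Feature | Tamsulosin | Silodosin | Difference (points) | p for the factor |
|---|---|---|---|---|
| Symptom-to-CT under 1 week | 67/77 = 87.0% | 37/102 = 36.3% | 50.7 | 6×10⁻¹¹ |
| Right side | 65/77 = 84.4% | 52/102 = 51.0% | 33.4 | 3×10⁻⁶ |
| Mid-ureter | 8/77 = 10.4% | 38/102 = 37.3% | 26.9 | 0.0003 (position) |
| Distal ureter | 41/77 = 53.2% | 38/102 = 37.3% | 16.0 | same test |
| Normal BMI | 72/77 = 93.5% | 94/102 = 92.2% | 1.3 | 0.73 |

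For a feature present in half the patients, the chance SD of such a difference is √[0.25·(1/77 + 1/102)] = 7.5 points. Symptom duration, side and position lie well beyond chance; BMI does not. Water intake also differs (76.6% v 48.0% under 1 litre), but it is not in the listed entry data and its timing is not given, so it is left out here.

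**3. What a size imbalance would do to 4-week expulsion.** With no drug effect, false difference = imbalance in the share under 5 mm × (small-stone rate − large-stone rate).

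- Smallest gap: 71 − 53 = 18 points.
- Midpoint gap: 84.5 − 39 = 45.5 points.
- Largest gap: 98 − 25 = 73 points.

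| Imbalance | Smallest gap | Midpoint | Largest gap |
|---|---|---|---|
| 10 points | 1.8 | 4.6 | 7.3 |
| 20 points | 3.6 | 9.1 | 14.6 |
| 30 points | 5.4 | 13.7 | 21.9 |

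To create the planned 19 points, the imbalance must be 19/0.73 = 26 points at the largest gap or 19/0.455 = 42 at the midpoint. It cannot do so at the smallest gap (19/0.18 exceeds 100).

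With 77 and 102 patients, half of all stones small and no drug effect, a 20-point imbalance gives a significant result in about 7%, 24% and 51% of trials at the three gaps.

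**4. Could size explain the reported difference?** Removal before 14 days is 52/102 − 6/77 = 51.0 − 7.8 = 43.2 points. Applying the passage-rate gaps to this early window, which is only a rough device, the imbalance needed is 43.2/0.73 = 59 points at the largest gap and 43.2/0.455 = 95 at the midpoint. By day 21 the difference is 89/102 − 20/77 = 61.3 points, which needs 84 at the largest gap and is impossible at the midpoint. No tabulated imbalance exceeds 51 points.

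On the time scale, with assumed window midpoints of 7, 17.5 and 25 days:

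- Tamsulosin: (6·7 + 14·17.5 + 57·25)/77 = 22.2 days.
- Silodosin: (52·7 + 37·17.5 + 13·25)/102 = 13.1 days.
- Gap: about 9 days.

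The only expulsion times by size in the document, from a silodosin cohort cited in the Discussion, are 9.56 and 11.33 days: a gap of 1.8 days.

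**5. Which outcome can be adjusted?** The removal windows sum to 6 + 14 + 57 = 77 and 52 + 37 + 13 = 102. Every tabulated patient has a removal time by day 28, so 4-week clearance has no non-events in these patients.

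**The case against.** A reader might infer that a size imbalance produced the reported superiority of silodosin. The documents do not support that. They give no size distribution, so no imbalance is known, and the imbalance required exceeds any that is tabulated. The Results also contradict themselves on whether the log-rank comparison was significant, so the difference to be explained is itself unsettled.

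Four other objections have force:

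- **Different outcome.** The cited figures are passage rates, while the reported contrast is in time. The 4.6 points per 10 therefore illustrate the planned 4-week outcome and do not correct the reported result.
- **Loose range.** The Introduction does not tie its rates to a treatment, and the largest gap pairs opposite extremes. Applying them to two alpha-blocker arms is an assumption.
- **Size is not the only factor.** Position and symptom duration are visibly imbalanced and are also named as affecting removal. Adjusting for size alone would leave them uncorrected.
- **Clearance models.** A risk difference is zero in every stratum, and a logistic model cannot be fitted, where all patients cleared.

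These points limit the claim and shape the remedy. They do not answer the omission. Nor does randomisation: no stratified allocation is described, and symptom duration, side and position are already imbalanced beyond chance.

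**Conclusion.** The point holds as a gap in analysis and reporting. A predictor that the document itself treats as strong was collected, is not shown by arm and enters no comparison, in arms whose other pre-treatment features differ by up to 51 points. An unseen size imbalance could bias the comparison in either direction or partly explain it.

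The size of the effect is a range, not an estimate: about 4.6 points of 4-week expulsion difference per 10 points of imbalance (1.8 to 7.3), against a planned 19. It assumes that the cited passage rates apply equally in both arms. Size alone is unlikely to account for the whole reported difference in time. The change should be made, but the omission does not by itself overturn the result.

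**What to change.** 1. Report stone size by arm (mean, SD, share under 5 mm), and age by arm.
2. Replace the unadjusted comparison with one adjusted for size in mm together with position and symptom duration. For time to expulsion, use a Cox model if dates are held, or a grouped-time model if only the windows are. A size-stratified log-rank test is a simpler alternative, but it does not deal with position and duration.
3. No tamsulosin patient is in the longest symptom-duration category (0 v 9), so merge it with the one below or use duration in days.
4. For 4-week clearance, give an adjusted or Mantel-Haenszel risk difference where non-cleared patients exist. If the analysis set has none, say so.
5. Show results by arm within <5 mm and 5 to <10 mm.
6. Because results are already reported, label the adjusted analysis as post hoc and justify the covariates by the Introduction's list of factors.

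This is a free improvement: two table rows, one model and one stratified display from data already collected, assuming that size was recorded completely. Adjustment would not repair a failure of allocation or follow-up, but it would let readers see how far size matters.
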